This is a quasi-experimental, longitudinal and prospective clinical trial, which will be carried out in patients who have suffered an ischemic stroke and who were treated in the neurology unit of the Lucus Augusti University Hospital, where this same study will be carried out.

The main objective of the study is to determine the effect of a nursing intervention based on health education on quality of life and symptoms of depression in people who have suffered an ischemic stroke.

To achieve this objective, variables such as cognitive status, symptoms of depression, autonomy and ability to perform in basic activities of daily living, neurological deficit and quality of life will be assessed.

Regarding the total number of subjects under study, according to the Atlas of Stroke in Galicia published by the Spanish Society of Neurology in 2018, the autonomous community of Galicia had a population of 2,701,819 inhabitants. Applying an incidence rate of 187.4 cases per 100,000 inhabitants, according to the IBERICTUS study, 5,064 new cases of stroke are estimated each year in Galicia per 100,000 inhabitants. The province of Lugo has 324,842 inhabitants on 1 January 2024, according to the INE, which, applying the same incidence rate, estimates 609 new cases of stroke per 100,000 inhabitants per year. Considering the proportion of ischemic strokes compared to other types of strokes 80:20, the estimated cases of the same would be 487 new cases in Lugo. The representative sample size of stroke patients in the province of Lugo would be 70 patients, 35 patients receiving the intervention and 35 controls.

Términos MESH: Ischemic Stroke; Nursing; Depression; Anxiety; Health Education; Quality of Life

Background and justification of the project

Stroke is defined as a syndrome with rapid onset of a focal neurological deficit of vascular origin. Classically, strokes are divided into two large groups: ischemic strokes, which will occur 80-85% of the time, and hemorrhagic strokes, which account for 15-20% of strokes. Specifically, ischemic stroke is defined as an episode of neurological dysfunction caused by focal cerebral infarction delimited by an occluded artery that decreases cerebral blood flow. Its etiology classification can be differentiated into five main subtypes: atherothrombotic stroke of large artery, cardioembolic stroke, lacunar of small vessel, stroke of rare cause and stroke of undetermined origin. In any case, as a consequence there will be an area of ischemia at risk of cell death and an infarcted area already necrotic, causing irreversible damage. The functional evolution of the patient after a stroke is classically established in three periods. An acute period that goes from the onset of symptoms to hospital discharge, a subacute period in which there is a progressive functional improvement, which continues in most cases during the first 3-6 months and finally a chronic phase of functional stabilization. Epidemiologically speaking, stroke is the second cause of death and third cause of disability worldwide and the first in Europe, with its incidence and prevalence being higher in women. While it is true that on the one hand there is a decrease in mortality in developed countries, on the other hand, there is an increase in the incidence associated with aging and an increase in life expectancy. For this last issue, it is estimated that mortality from ischemic stroke will increase in Spain by about 39% between 2015 and 2035. In Spain in 2022, cerebrovascular disease accounted for 48% of total admissions due to a neurological cause. It affects 1.5% of people, increasing to 3% from the age of 65 and to 10% from the age of 80. In Europe, the sex-adjusted

incidence of stroke was 191.9 per 100,000 person-years and the sex-adjusted prevalence was 9.2%. In 2019, the total number of disability-adjusted life years related to stroke exceeded 125 million worldwide.

Economically, ischemic stroke accounts for 3-4% of health expenditure in Western countries and is expected to quadruple in the future.

The main deficits, disabilities and complications observable after a stroke include paralysis, emotional imbalance, speech and language disorders, visual disturbances, cognitive deficits, physical and mental fatigue, epileptic seizures and pain. The greatest risk factor predicting poor prognosis of ischemic stroke is age, which is directly related to epidemiological data.

Ischemic stroke is the leading cause of acquired disability in adults. Two out of three people affected by a stroke associate difficulties in basic tasks such as showering or bathing without help and in household chores. A high percentage of these people perceive their state of health as fair (37.3%), or bad or very bad (36.5%) and a majority suffer pain or discomfort (62.4%) and difficulties in carrying out their daily activities (59.1%).

The mental health of those who have suffered a stroke is also severely affected, with women and those over 65 scoring significantly worse. It is estimated that between 20 and 50% of stroke survivors develop depressive symptoms at some point, which can have a direct impact on the patient's physical and cognitive recovery. The manifestation of post-stroke depression includes everything from persistent sadness to loss of interest in activities that the patient previously enjoyed, changes in appetite or difficulties concentrating or falling asleep. In the same way, dysphagia, a common complication after an ischemic stroke, is also related to the appearance of depressive symptoms. Other risk factors have been described when it comes to developing symptoms of depression in patients who have suffered a stroke, such as low educational level or low economic level. Early identification and treatment of depression in post-ischemized patients is crucial for improving their quality of life and early rehabilitation.

Patient function after stroke is associated with the likelihood of hospital readmission. Patients with poor function at discharge are more likely to need long-term care and intensive rehabilitation plans. Functionality includes the interaction of positive aspects between the 3 main components: body functions and structures; activity and participation; and environmental and personal factors. Post-stroke functionality has not yet been comprehensively assessed. Some authors postulate a progressive functional improvement beyond 12 months when accompanied by rehabilitation treatment and, on the contrary, a progressive functional deterioration in the absence of specific rehabilitation therapy.

The greatest attention to stroke patients has commonly focused on the acute phase, which has managed to reduce morbidity and mortality. However, studies focused on the subacute phase are less frequent and few are those that focus on long-term evolution. Other authors postulate that differences in functional status at three months are associated with significant differences in survival and performance status during a seven-year follow-up.

In relation to the subacute phase, the evaluation of the functional status of ABVD is recorded in only 24.6% of cases at discharge and for six months after the episode.

To assess the autonomy of stroke patients, it is necessary to consider how the physical, cognitive, and psychological impacts of stroke may lead to a wide range of activity limitations and participation restrictions.

Patients who have suffered a stroke are often predisposed to a sedentary lifestyle that affects performance in activities of daily living, thus increasing the risk of relapse. Resuming activities of daily living is therefore of great importance for life satisfaction and is considered as a primary goal for rehabilitation. The first six months after stroke are therefore considered critical for rehabilitation. Rehabilitation plays a fundamental role in this

process since it directly influences the reduction of disability and handicap by reducing the personal, family and social cost, and its usefulness is fully established.

The functional evolution varies with the initial clinical severity. Maximum functionality is reached on average at 2 months in patients with initially mild strokes, at 3 months in patients with moderate strokes, at 4 months in severe strokes and at 5 months in very severe strokes. In addition, several studies have shown that functional outcome after stroke is a potent predictor of long-term mortality, therefore, we need to promote maximum functional independence of stroke survivors living at home through supervised and tailored nursing interventions and physical activities. Results from previous studies indicate that Barthel's delta, i.e. the change in a patient's functional autonomy, is equal to 0 for those interventions performed in routine clinical practice other than treatment with rt-PA or thrombectomy after suffering from an ischemic stroke. Therefore, it can be deduced that they are not having a clear or optimal effect on functional improvement in those patients who have suffered an ischemic stroke.

Experts recommend a series of services and resources for a good functional recovery of patients who have suffered a stroke. Among other issues are training and health education programs. In this way, the nursing profession is trained to formulate personalized comprehensive care plans, promote comprehensive recovery, and strengthen communication with patients and their families. Nurses should perform interventions in accordance with general practice to provide continuity of care for stroke patients throughout the patient's recovery journey. Integrated care is desirable and constitutes a reference model for all situations considered. Planning for teaching and discharge from hospital can help families of patients who have suffered a stroke to make specific long-term arrangements for the expected functional outcome. In addition, post-discharge follow-up and support interventions should be implemented that are individualized to the caregiver's needs. Early rehabilitation intervention and evidence-based nursing interventions showed significant improvements in their scores on tests related to cognitive impairment and neurological deficit, as well as improved disability. However, there are hardly any standardized, approved and scientifically proven health education programs. The application of nursing interventions, through health education, to minimize the levels of depression caused by the disease, to two groups, case and control, will allow us to evaluate the influence of health education on the symptomatology of depression and improve the quality of life in patients who have suffered an ischemic stroke.

Study hypothesis

A nursing intervention based on health education will improve quality of life and reduce the symptoms of depression in patients who have suffered an ischemic stroke.

Objectives

General objective: to determine the effect of a nursing intervention based on health education on quality of life and depression symptoms in people who have suffered an ischemic stroke.

Specific objectives:

1. To assess and compare the level of depression in patients who have suffered an ischemic stroke.
2. To assess and compare the degree of autonomy and level of functional dependence of patients who have suffered an ischemic stroke.
3. To assess and compare the cognitive status of patients who have suffered an ischemic stroke.
4. To assess and compare neurological deficits of patients who have suffered an ischemic stroke.

5. Assess and compare the risk of bronchoaspiration, the presence of pressure ulcers, swallowing, blood pressure, temperature and glucose level and assess the level of pain.
6. To correlate the cognitive state and the level of depression symptomatology with implemented variables.
7. To reduce the psychological impact of depression in patients who have suffered an ischemic stroke who have received health education.
8. To compare the level of depression symptoms in patients who have suffered an ischemic stroke who received health education with those who did not.

Type of study

It is a quasi-experimental, longitudinal and prospective clinical trial.

Material and methods

Scope of study

For the preparation of this study, the target population was patients who have suffered an ischemic stroke for the first time and were treated by physicians from the Neurology and Neurosurgery Service of the Lucus Augusti University Hospital (HULA).

Definition of the subjects to be studied

A representative sample size of patients who have suffered an ischemic stroke for the first time and treated by physicians from the Neurology and Neurosurgery Service of the HULA will be collected. From this sample, 2 groups will be extracted: the group to which a health education program will be applied and the control group to which this program will not be applied.

Subject selection and withdrawal

Inclusion criteria: anterior or posterior cerebral occlusion, age ≥ 18 years.

Exclusion criteria: intracranial hemorrhage, pregnancy, cognitive inability to participate, non-acceptance to participate in the study and administer questionnaires.

Recruitment and recruitment of participants

Prior to the recruitment process, the required informed consent signed by said participant will be obtained. Next, the variables will be collected. The recruitment of participants will be carried out by the principal investigator and collaborating researchers of the study in the neurology and neurosurgery ward:

- [name]
- [name]
- [name]
- [name]

The tasks "*Bibliographic Review, Study Design, Documentation Presentation, Database Design*" will be carried out by the collaborating researcher [name] supervised and in collaboration with the collaborating researchers [name] and [name].

The recruitment of patients and immediate data will be carried out consecutively on the neurology and neurosurgery floor of the HULA by the collaborating researchers [name], [name], [name] and the principal investigator [name] and by the collaborating researcher in neurology consultation at the HULA [name].

The performance of the sessions is conditioned by the time of diagnosis of the stroke. In this way, it is necessary to recruit a minimum group of patients to carry out the workshops according to the established methodology. Subsequently, these will be carried out by the collaborating researcher [name]. After 3 and 6 months following the workshops, the same researcher together with the collaborating researcher [name] will carry out the follow-up and reevaluation in the neurology consultation of the HULA.

Finally, the process of integrating data and statistical analysis together with the final task of writing results, discussion and conclusions and their dissemination will be carried out by the collaborating researcher [name].

First, the initial evaluation of the patients will be carried out for the collection of variables to be studied in the neurology and neurosurgery floor of the HULA. Subsequently, recruitment will be carried out after delivering a sheet with all the information and the due consent document and they will be scheduled in outpatient clinics where the intervention of this study will be applied.

Assignment/Randomization Procedure

The procedure for assigning the members of each group will be random and the EPIDAT program will be used to make this selection.

Justification of the sample size

According to the Atlas of Stroke in Galicia published by the Spanish Society of Neurology in 2018, the autonomous community of Galicia had a population of 2,701,819 inhabitants. Applying an incidence rate of 187.4 cases per 100,000 inhabitants, according to the IBERICTUS study, 5,064 new cases of stroke are estimated each year in Galicia per 100,000 inhabitants. The province of Lugo has 324,842 inhabitants on 1 January 2024, according to the INE, which, applying the same incidence rate, estimates 609 new cases of stroke per 100,000 inhabitants per year. Considering the proportion of ischemic strokes compared to other types of strokes 80:20, the estimated cases of the same would be 487 new cases in Lugo.

In relation to the calculation of the sample size, the following formula is applied.

$$n = \frac{\left[Z_{1-\frac{\alpha}{2}} \sqrt{2p(1-p)} + Z_{1-\beta} \sqrt{p_1(1-p_1) + p_2(1-p_2)} \right]^2}{(p_1 - p_2)^2}$$

Where:

- P2 (frequency of exposure between controls) = 0.4
- OR=4
- Assuming a 1:1 ratio of controls per case
- n = participants as the minimum sample size.

Assuming the calculations, the representative sample size of stroke patients in the province of Lugo would be 70 patients, 35 patients receiving the intervention and 35 controls.

Primary and secondary variables

Independent variables:

- Socioepidemiological: sex, age (< 65 years, 65-80 years, >80 years), date of ischemic event.
- Clinical Signs: type of stroke, treatment modality (received rt-PA or mechanical thrombectomy according to the candidates' protocol), number of falls, degree of pain, presence of pressure ulcers, genesis of new pressure ulcers, episodes of bronchoaspiration, presence of pneumonia, presence of dysphagia, vital signs (blood pressure, glycemia, temperature).
- You receive health education after a stroke or do not receive health education after a stroke.

Dependent variables:

- Assessment of cognitive status by scoring the Mini Mental State Examination (MMSE) questionnaire.
- Assessment of depression symptomatology by scoring on the Beck questionnaire (BDI) or also called depression self-report inventory.
- Assessment of autonomy and ability to perform in basic activities of daily living by means of a score from the Barthel Index.
- Neurological deficit using the NIHSS scale.
- Assessment of quality of life by scoring on the European Quality of Life Scale.

Instruments

This section lists the instruments that will be used to measure the variables under study. They are described in a more extensive manner in Annex I.

1. Mini mental status examination (MMSE).
2. Beck Questionnaire (BDI).
3. Barthel index.
4. National institute of Health Stroke Scale (NIHSS).
5. Visual Analog Scale (VAS)
6. European Quality of Life Scale (EQLS).

Description of the intervention

The initial evaluation of the patients will be carried out for the collection of the variables to be studied upon admission. Subsequently, 2 groups will be established: the group to which a health education program will be applied (intervention of this study that will be specified below) and the control group. Finally, a follow-up is proposed at 3 and 6 months after the health education intervention to collect data related to the chronic/stabilization phase in post-stroke recovery.

Nursing intervention: Health education for post-stroke patients

Objectives

- Learn to identify and recognize prodromal symptoms of a new ischemic event.

- Identify what changes have occurred or may occur in patients after the sequelae of the ischemic event and how they may impact their daily lives.
- Describe the recommended care that patients can incorporate into their daily lives to reduce the impact of sequelae and improve their quality of life.
- Learn to recognize and manage early signs and symptoms of low mood and depressive symptoms.

Methodology

The sessions taught are based on meaningful learning, also supported by constructivist, cognitivist and behavioural learning.

The program consists of 3 fundamental pillars: session 1. *Early symptoms of stroke and recognition*, session 2. *Living with stroke: the day-to-day care*, session 3. *Mood management*. In addition, a workshop (session 4) will be designed for intervention in depression based on the development of coping tools through full breathing techniques, relaxation techniques, psychotherapy and mindfulness. All sessions will preferably be group. The contents of these sessions are detailed in Annex II.

Taking into account that 35 patients will receive the health education program, it is estimated that 3-4 groups of 8-12 people distributed independently in the sessions taught by the same instructor.

Materials

- Classroom for health education at HULA.
- Physical and digital support to support the sessions.

Time scheduling

The sessions will be divided into two different days.

Day 1 (40 minutes)

- Session 1: Early symptoms of stroke and recognition of these.
- Session 2: Living with stroke: the day-to-day care.

Day 2 (40 minutes)

- Session 3: Mood management and depression.
- Session 4: relaxation workshop with guided meditation (mindfulness)

Timeline and expected completion date.

Once the Santiago-Lugo Research Ethics Committee issues this research plan as favorable, the study will begin following the following schedule:

Task	July and August 2025	September 2025 to November 2025	November 2025 to May 2026	June to August 2026	September 2026 to January 2027	February to December 2027	January 2028 to September 2028
Literature review							
Study design							
Submission of documentation							

Database design							
Patient recruitment and immediate data							
Conducting the workshops							
Follow-up 3 months							
Follow-up 6 months							
Data integration and statistical analysis							
Results, discussion, conclusions							
Scientific dissemination							

The tasks "*BibliographicReview, Study Design, Presentation of Documentation, Database Design*" will be carried out by the collaborating researcher [name].

The recruitment of patients and immediate data will be carried out consecutively on the neurology and neurosurgery floor of the HULA by the collaborating researchers [name], [name], [name] and the principal investigator [name] and by the collaborating researcher in consultation of the neurology of the HULA [name].

The performance of the sessions is conditioned by the time of diagnosis of the stroke. In this way, it is necessary to recruit a minimum group of patients to carry out the workshops according to the established methodology. Subsequently, these will be carried out by the collaborating researcher [name]. After 3 and 6 months following the workshops, the same researcher together with the collaborating researcher [name] will carry out the follow-up and reevaluation in the neurology consultation of the HULA.

Finally, the process of integrating data and statistical analysis together with the final task of writing results, discussion and conclusions and their dissemination will be carried out by the collaborating researcher [name].

The collaborating researchers [name] and [name] will be in charge throughout the research process of the work surrounding it with respect to the contribution to the conception and design of the work, acquisition and analysis of the study data, critical review with important intellectual input, responsibility for the accuracy and completeness of the research, supervision, final approval, and project management.

Statistical analysis plan

A descriptive analysis will be carried out using measures of central tendency, such as mean (M), and dispersion, using standard deviation (SD), to examine quantitative variables. In the case of qualitative variables, absolute frequencies and percentages will be used. To determine the correlation between groups, the Chi-square test (χ^2) will be applied to the qualitative variables. Regarding the quantitative variables, the Kolmogorov-Smirnov test will begin to evaluate the normality of the distribution (n=70). If the quantitative variables show a non-parametric distribution, the Kruskal-Wallis test will be used to compare more than two groups, while the differences between pairs will be analyzed using the Mann-Whitney U test. If they are parametric, it will be appropriate to resort to ANOVA, Tukey and Bonferroni. The association between the variables will be evaluated in terms of strength and direction using Spearman's correlation coefficient. Distracting factors (age and sex) that usually tend to normal will be tested with ANOVA and Levene. The effect of the intervention will be determined using relative risk (RR) Statistical analyses will be performed using PASW Statistics software (version 23.0; SPSS Inc., Chicago, Illinois), establishing a bilateral significance level of $p<0.05$.

Ethical-legal aspects

Compliance with Good Clinical Practice Standards, Declaration of Helsinki, Oviedo

Convention, as well as data protection regulations, management of medical records and other applicable regulations depending on the type of study.

The review and approval of the research plan by the Santiago-Lugo Research Ethics Committee is requested, following local and international regulations in the field of medical research and the standards established by the Declaration of Helsinki. The development of this thesis will be carried out respecting the Declaration of Helsinki of the World Medical Association of 1964 and ratifications of the following assemblies on ethical principles for medical research on human beings, and the Convention on Human Rights and Biomedicine, signed in Oviedo on April 4, 1997 and successive actions. The researchers participating in this study undertake that all clinical data collected from the study subjects will be separated from the personally identifiable data, so that the anonymity of the patients is ensured; respecting the Law on the Protection of Personal Data and Guarantee of Digital Rights (Organic Law 3/2018, of 5 December), Law 41/2002, of 14 November (basic regulation of patient autonomy and rights and obligations in terms of clinical information and documentation), as well as Law 3/2001, of 28 May (regulating informed consent and clinical documentation), as well as Law 3/2005, of 7 March, amending Law 3/2001 and Decree 29/2009 of 5 February, which regulates access to electronic medical records. The patient's data will be collected by the investigator in the study-specific data collection notebook (CRD). Each CRD will be encrypted, protecting the patient's identity. Only the research team and the health authorities, who have a duty to maintain confidentiality, will have access to all the data collected for the study. The data controller will be the HULA. Information may only be transmitted to third parties that cannot be identified. Once the study is completed and the thesis is finished, the data collected will be destroyed or kept anonymous for use in future research according to what each participant chooses in the signing of the consent. An Information Sheet will be provided to the participants and informed consent. Information regarding the identity of patients will be and is considered confidential for all purposes. In order to properly maintain confidentiality with respect to patient information, an appropriate coding and identification dissociation will be carried out in the database, so that only the researcher may associate such data with an

identified or identifiable person. The database that will generate the study will not contain any identification of the patient. Once the study is complete, the database will be deleted. With regard to the data of the study, the provisions of the Organic Law on "Protection of Personal Data" in force will be followed.

Informed consent models.

The informed consent forms have been drafted, to be delivered individually to the participants.

Confidentiality of the information collected in the context of the study.

In order to properly maintain confidentiality with respect to patient information, an appropriate coding and identification dissociation will be carried out in the database, so that only the researcher may associate such data with an identified or identifiable person. Once the study is completed, the data will be deleted or kept pseudonymized as selected by the patient in the Consent.

Commitment to publish results

The researcher undertakes to disseminate the results of his or her research, whether positive or negative.

Economic report and source of funding

Not applicable.

Bibliography

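### Acute reperfusion treatment is a listed variable that the protocol links to Barthel change, but Annex III has no field for it and the analysis section names only age and sex as factors

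*Protocol*

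**What the plan says.** - **Background and justification of the project:** citing previous studies, the protocol says that the change in Barthel "is equal to 0 for those interventions performed in routine clinical practice other than treatment with rt-PA or thrombectomy".
- **Objectives:** autonomy and functional dependence are compared under specific objective 2. The general objective is quality of life and depression symptoms.
- **Assignment/Randomization Procedure:** "The procedure for assigning the members of each group will be random and the EPIDAT program will be used to make this selection". No stratum or balancing factor is named.
- **Justification of the sample size:** "70 patients, 35 patients receiving the intervention and 35 controls".
- **Primary and secondary variables:** the independent variables include "treatment modality (received rt-PA or mechanical thrombectomy according to the candidates' protocol". The Barthel Index is a dependent variable.
- **Statistical analysis plan (section of the protocol):** "Distracting factors (age and sex) that usually tend to normal will be tested with ANOVA and Levene". No other factor is named.
- **Annex III, first grid:** there are columns for sex, age, event date, event type, BDI and MMSE at three time points, Barthel, NIHSS, vital signs, swallowing, breathing, pressure ulcers and pain. No column is recognisable as treatment received. rt-PA occurs only in the heading of one BDI and one MMSE time point. Thrombectomy does not occur.

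**The concern.** The protocol takes three steps that do not join up. It singles out rt-PA and thrombectomy as relevant to Barthel change and lists them as a variable to be used. It then provides no place to record them and does not name them among the factors to be examined.

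With 35 patients per arm, the reperfused share will often differ somewhat between arms by chance. If the treatment predicts Barthel, leaving it out of the analysis costs precision. If the realised trial happens to be unbalanced, a reader will ask whether the functional difference reflects acute treatment. The form as drafted offers no answer.

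**Working it through.** **1. The arm size.** The inputs are "P2 (frequency of exposure between controls) = 0.4", an odds ratio of 4, a 1:1 ratio and a two-sided 5% level. Power is not stated; 80% is assumed.

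- p1 = 4 × 0.4 / (1 − 0.4 + 4 × 0.4) = 1.6 / 2.2 = 0.727.
- The printed formula then gives n = 34.84, so 35 per group and 70 in total. The stated size reproduces and is used below.

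**2. Variable list against form.** Treatment modality is in the list and has no dedicated column in the grid. rt-PA receipt might be guessed from whether the two rt-PA time-point columns are filled, but a blank could mean no rt-PA or a missed assessment. Thrombectomy cannot be inferred at all. This step needs no assumption.

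**3. How large a chance imbalance is.** The protocol gives no reperfusion rate, so 20-50% is assumed. With K reperfused patients among 70, split 35/35 at random, the count per arm is hypergeometric. With p = K/70, the SD of the gap in shares is 2 × √(p(1 − p)/69).

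| Assumed share | SD of gap (points) | P(gap ≥ 10 points) | P(gap ≥ 20 points) |
|---|---|---|---|
| 20% | 9.6 | 0.37 | 0.03 |
| 30% | 11.0 | 0.30 | 0.12 |
| 40% | 11.8 | 0.47 | 0.09 |
| 50% | 12.0 | 0.34 | 0.15 |

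The columns do not rise steadily because only odd or only even gaps are possible for a given K.

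**4. What a gap does to Barthel.** Assume reperfused patients score D = 10 to 20 points higher. A 20-point gap then shifts the mean difference by 0.20 × 10 = 2 to 0.20 × 20 = 4 points. With an assumed within-group SD of 25, the standard error of the difference is 25 × √(2/35) = 5.98. Even this uncommon gap moves the estimate by one third to two thirds of a standard error.

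**5. Cost of not adjusting.** The ratio of unadjusted to adjusted standard error is about √(1 + D² p(1 − p)/25²).

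- p = 0.2, D = 10: √(1 + 16/625) = 1.013.
- p = 0.2, D = 20: √(1 + 64/625) = 1.050.
- p = 0.5, D = 10: √(1 + 25/625) = 1.020.
- p = 0.5, D = 20: √(1 + 100/625) = 1.077.

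So the standard error is about 1-8% larger.

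**6. Check on bias and error rate.** For each combination of a 30% or 40% share and D = 10 or 20, 20,000 trials were simulated with no intervention effect. The mean unadjusted difference lay between −0.06 and 0.08 Barthel points, which is zero within simulation error. Type I error was 0.047 to 0.050. The standard error was 6.03 to 6.46 unadjusted and 5.96 to 6.05 with treatment as a covariate. The ratio of about 1.01 to 1.07 agrees with step 5.

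**The case against.** The strongest reply is that unstratified randomisation is not an error. That stands. Chance imbalance is already part of the standard error, and step 6 shows no bias and no inflation of the error rate. A reader might infer that the functional comparison is distorted by the allocation scheme; the documents do not support that.

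Three further replies also stand in part.

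- **The premise should not be over-read.** A reader might conclude that rt-PA and thrombectomy are the only routine care that changes Barthel. The same background calls the usefulness of rehabilitation fully established, says functional course varies with initial severity, and names age as the greatest risk factor for poor prognosis. Severity and age have at least as good a claim to be strata. The background sentence also concerns Barthel only, so it gives no basis for extending the point to NIHSS.
- **The sizes rest on assumptions.** The reperfusion rate, the Barthel effect and the SD are not in the protocol. Because treatment precedes ward recruitment, a Barthel score taken there may already carry part of its effect, and the later difference could be smaller than assumed.
- **The grid is incomplete in general.** It also lacks columns for falls, pneumonia and study group, and some translated headings are obscure. Treatment received could be retrieved from the chart while patients remain linkable, and a separate analysis plan may add covariates.

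None of this removes the mismatch. A listed variable still needs a field, and retrieval becomes uncertain after the study, when the protocol says data are to be deleted or kept without identification.

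**Conclusion.** The point holds as a gap between the variable list and the collection form, with a modest statistical cost. Treatment modality is a planned variable that the protocol itself connects to Barthel, it has no dedicated field, thrombectomy is not on the grid, and the analysis section names only age and sex.

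The cost is a standard error about 1-8% larger for the Barthel difference, under the assumed 20-50% reperfused, 10-20 point effect and SD of 25, and no means of showing or adjusting for a chance imbalance from the form. It bears on specific objective 2. Nothing in the protocol ties reperfusion to the general objective of quality of life and depression.

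A reader might go further and hold that allocation must be stratified by reperfusion. That does not follow. Randomisation is valid as planned, and the choice of stratum is open. In a single-centre trial where the education group is evident to all, small blocks would also make upcoming assignments easier to guess.

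**What to change.** - Add one field to the Annex III grid: acute treatment received (none / rt-PA / thrombectomy / both), completed at the initial evaluation.
- State in the analysis section that this field is a prespecified baseline covariate in the between-arm Barthel comparison. Say in advance that it is collapsed to any / none if categories are sparse. The planned ANOVA extends to a model with a covariate. The Mann-Whitney test takes none, so if the normality check leads there, an ordinal or rank-based model that carries the covariate should be named.
- Show the field by arm in the baseline table.

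The cost is one form field and one sentence. The treatment has already been given and is already a listed variable, so no patient, visit or procedure is added and the sample size is unchanged. The field should be in place before data collection starts.

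Stratified allocation is optional. With permuted blocks of 4, it would hold the gap in the reperfused group to at most 2 patients (2/35, about 6 points), to be weighed against the predictability just noted.
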